1. Title of Project:

Awake caudal catheter infusion versus general anesthesia and single-dose caudal injection for preterm NICU patients undergoing inguinal herniorrhaphy.

2. Principal Investigator: [name], MMS, Nemours Pediatric Surgery

Co-Investigator(s): [name], Nemours Anesthesiology and [name], DO. University of Florida Neonatology

3. Abstract:

This is a prospective, blinded, randomized controlled trial evaluating the effectiveness of awake caudal catheter infusion versus single dose caudal injection and general anesthesia in the surgical management of preterm infant inguinal hernia repair. Currently, the standard of care in the United States is general anesthesia. Spinal anesthesia has been advocated for but highly rejected in the pediatric surgical community due to its high failure rate which can be up to 28%. Spinal anesthesia is a form of regional anesthesia involving injection of a local anesthetic into the subarachnoid space, via a fine needle, in a single injection. The failure rate has to do with the time constraint of spinal anesthesia which is approximately 1 hour. It is difficult to perform a bilateral inguinal hernia in that time duration, necessitating a return trip to the operating room for the contralateral side or intubation midway through the surgical case. We hypothesize that awake caudal catheter infusion will allow for the following benefits (1) greater than 2 hour anesthetic time via redosing which will allow for the completion of the planned surgical procedure (2) exhibit a negligible failure rate (3) minimize post-operative complications that have been associated with general anesthesia in the preterm neonate.

4. Background:

It is well established that preterm inguinal hernias discovered in the NICU pose a significant surgical risk due to the associated co-morbid conditions that accompany these patients. There have been studies that have established that elective outpatient repair of inguinal hernias found in the NICU can be safely performed. However, due to the low associated risk of incarceration and subsequent bowel loss many institutions are reluctant to treat this way and practice is widely variable (Sulkowski JP, 2015). The most common practice in NICUs across the country is to wait until the patient is ready for discharge from the NICU and to perform inguinal hernia repair prior to discharge (Crankson SJ, 2015). This allows for the patient to undergo significant growth in the NICU without increasing the risk of incarceration. Currently and historically this operation is performed under general anesthesia, which requires the preterm neonate to be intubated during the procedure and depending on their respiratory status, sometimes afterward. A recent review of current practices in regards to inguinal hernia repair in the United States demonstrated that 70% of repairs are performed with general anesthesia (Wiener ES, 1996). Due to the known risk of apnea and bradycardia in the preterm infant, alternatives to general anesthesia for inguinal hernia repair has been hotly debated in the surgical, anesthetic, and neonatology literature. General anesthesia with single-shot caudal injection is an established practice with demonstrated safety. A study utilized this technique where 91 out of 126 patients safely underwent general anesthesia and caudal injection (Murphy, 2008). Recent studies suggest that low gestational and postconceptional age, low birth weight, anemia, and complicated past medical history affect respiratory complication rates, particularly apnea in formerly premature infants undergoing elective inguinal hernia repair (Ozdemir T, 2013). Spinal anesthesia is currently the most common anesthetic procedure used in the surgical treatment of preterm inguinal hernias after general anesthesia, although spinal anesthesia is not currently in wide surgical practice due to its high failure rate that is up to 28% in some studies (López T, 2012). Spinal anesthesia in the preterm infant has been found to decrease apneic events as well as decrease post-operative prolonged mechanical ventilation, although the latter is disputed in the literature (G, 2003).

(Craven PD, 2003). A significant portion of this failure is due to the short duration of anesthetic time, which is less than 1 hour depending upon patient weight. Therefore, it is hard to make a surgical argument for its preferential use. An alternative to spinal anesthesia that results in an ability to sustain regional anesthetic effect for a longer duration is the caudal catheter infusion. Caudal anesthesia is hailed as the single most important regional anesthesia technique in children (M, 2015). Compared with neuraxial techniques in adults, it can be easily learned and reproduced (Schuepfer G, 2000). The caudal catheter technique has been previously reported in multiple publications and textbooks to safely provide post-operative neuraxial analgesia in pre-term/low-weight/neonatal patients. Caudal catheter technique involves placement of a small catheter under ultrasound guidance into the caudal epidural canal to allow re-dosing of local anesthetic during the case and has been shown to be safe and effective management in neonates (Somri M, 2007). Ultrasound guidance has been demonstrated to be fundamental for the performance of successful posterior approaches in pediatric patients (Kirchmair L, 2004). Ultrasound guided placement of caudal anesthesia is also successfully used in patients with difficult anatomy (Schwartz D, 2008). The use of peri-operative analgesic blocks has also been shown to result in quicker awakening and a more comfortable postoperative course (Conroy JM, 1993). Current literature has shown caudal anesthesia with a failure rate of less than 5% which is significantly less than spinal anesthesia (Geze S, 2011) (Marhofer P, 2015) (Wong SY, 2004) (Hosseini Jahromi SA, 2012). Currently, there is only one published article that has used single-injection caudal injection in the management of preterm NICU inguinal hernias (Geze S, 2011). There were no reported adverse events and no failures in a sample of 15 neonates.

If the results of the study support the hypothesis, this contribution could be significant and impact clinical practice and the standard of care by allowing surgeons to safely perform the operation in an adequate time period. In addition, it could decrease preterm neonatal post-operative complications, which are significant. In general, pediatric surgeons are leaders in surgical innovation which has been shown in the rapid advancement of laparoscopic techniques and minimally invasive procedures. Once it is established that the completion rate with awake caudal catheter technique in preterm infant hernias is high without increasing morbidity and mortality, there should not be a significant argument against its use. It has already been established that regional anesthesia has a significant benefit to the preterm infant (Tobias JD, 1992). As a prospective, randomized trial it also is attempting to reach the gold standard in clinical research as opposed to a retrospective trial. This research project is a study that other investigators could continue to build upon for its other possible indications. Awake caudal catheter technique is useful analgesia in procedures that occur below the level of the umbilicus. In other high-risk pediatric patients, this technique has the potential to be used in lower extremity surgical procedures as well as urologic procedures (Londergan TA, 1994). Caudal catheter placement is performed by a significant number of anesthesiologists, but the reinforcement of its benefits by this paper has the potential to increase its application and awareness among the community. The neonatologists' community as well as the NICU patients would benefit from solid evidence that the use of regional anesthesia can be effectively used as an alternative to general anesthesia in some surgical instances. Therefore, our study has the ability to change clinical practice in three distinct fields of medicine.

5. Specific Aims:

An elective operative procedure on preterm neonatal patients has long been debated among pediatric surgeons, neonatologists, and anesthesiologists. Anesthesia in this particular group of patients pose a significant risk due to their associated medical conditions which can be multiple and quite varied. The most common risk factor for these neonates undergoing general anesthesia is their inherent bronchopulmonary dysplasia which ranges from mild to severe. It is well

 - We hypothesize that awake caudal catheter technique when compared with single-dose caudal injection and general anesthesia will be of greater benefit to preterm infants via the following primary quantifiable measures: reduction in the time to return of baseline respiratory function, reduction in the number of apneic episodes (defined as cessation of breathing by a premature infant that lasts for more than 20 seconds and/or is accompanied by hypoxia or bradycardia), and a reduction in bradycardic events (heart rate <90).
 - We hypothesize that secondary measures will be of greater benefit to preterm infants as well with decreased days to hospital discharge, decreased number of post-operative narcotic use days, decreased mechanical ventilation days, and decreased time to full oral feeds.

Such results are expected to advance the field of pediatric anesthesiology and pediatric surgery which will impact clinical practice by changing the peri-operative management of high risk NICU patients.

6. Research Plan:

Inclusion and Exclusion Criteria

Patients included in the study are preterm infants in the NICU less than 50 weeks post gestational age born at less than 37 weeks gestational age. Patients will be within 1 week of meeting NICU discharge criteria with or without supplemental oxygen prior to surgical scheduling for inguinal hernia repair. Males and females will be included in this study, but there is a known higher incidence of male inguinal hernias in the literature, approximately 6:1.

Patients undergoing other invasive procedures including but not limited to gastrostomy tube placement, tracheostomy, and/or laser eye treatments will be excluded. Any patient with a medical condition that would prevent a regional anesthetic from being performed (i.e. bleeding diathesis, vertebral anomalies, spinal cord injury prior to surgery) and any contradictions to the prescribed medications in the protocol will be excluded.

This will be a prospective, blinded, randomized controlled clinical trial. When the NICU staff and surgeon decide that inguinal hernia repair is warranted, a research representative will approach the family for research consent. [name] and [name] will provide the anesthesia for both groups and will obtain anesthesia consent on the day of surgery. The general anesthesia and single-shot caudal group will be induced with intravenous (IV) propofol 3mg/kg and rocuronium 0.6mg/kg and intubated. Caffeine 15mg/kg and rectal Tylenol 30mg/kg will then be given for apnea prevention and pain control. Caudal will be performed under ultrasound guidance with bupivacaine 0.25% + 1:200,000 epinephrine (total dose 2.5mg/kg) prior to start of the surgery. At the conclusion of the operation, neuromuscular blockade will be reversed with neostigmine and glycopyrrolate. The patient will be extubated once criteria are met. If the patient is unable to extubate within 20-30 minutes, they will be transferred to the NICU intubated with assisted ventilation. The general anesthesia group will not receive narcotics for pain management intra-operatively due to the increased risk of apnea and bradycardia. Since the study is attempting to answer whether the act of exposure to general anesthesia changes the likelihood of apnea and bradycardia, we need to maintain the same approach to pain management in both groups. No Precedex will be given in the general anesthesia group. Pain management in the NICU will be the following: mild to moderate pain based on a FLACC scale will receive rectal or oral Tylenol, while moderate-severe pain will receive IV morphine 0.05mg/kg.

In the caudal infusion group, Precedex 0.5 mg/kg IV will be administered for sedation over 10 minutes and maintained with an infusion of 0.7 mg/kg/h. Under ultrasound guidance a 20 gauge angio-catheter will be placed into the caudal space and secured to the skin with a tegaderm. A low volume extension catheter will be connected to the angio-catheter and bupivacaine .3% + 1:200,000 epinephrine (dose 3mg/kg) will be administered via the catheter. An additional dose of 1mg/kg will be administered at 1 hour post initial dosing time to extend the duration of the caudal. Intravenous caffeine and rectal Tylenol will be administered for apnea prevention and additional pain control. If patient agitation is noted during the operation, an additional bolus of Precedex 0.5 mg/kg will be administered. If agitation persists, pain, and/or respiratory distress are noted during the operation, general anesthesia will be induced with propofol 3 mg/kg and rocuronium 0.6 mg/kg followed by endotracheal intubation. The angio-catheter will be removed at the end of the surgical procedure. Pain management in the NICU will be the following: mild to moderate pain based on a FLACC scale will receive rectal or oral Tylenol, while moderate-severe pain will receive IV morphine 0.05mg/kg.

Blinding of the study will occur on the day of surgery by the anesthesiologists. Prior to a patient arrival to operating room, the anesthesiologist will randomly draw an envelope from a folder that will allocate group assignment (this precludes bias while discussing patient care with parents and getting consent). It is estimated that we will need approximately 20 patients in each group. 10 envelopes at a time will be placed in the folder, 5 will be in the awake caudal catheter group and 5 will be in the general anesthesia and single-dose caudal group. This will keep the numbers equal when going forward with the study.

Intra-operatively, neither the anesthesiologist nor the surgeon will be blinded since they are present from the induction of anesthesia until the conclusion of the operation for patient safety. The pre-operative, intra-operative, and post-operative care by the NICU will be blinded. All patients will have had a caudal procedure (single vs. catheter) and extubation will be attempted in all patients prior to NICU transport. If extubation cannot be accomplished within 30 minutes following completion of the operation, the patient will be transported to the NICU intubated. Since post-operatively the same medical personnel cannot be used in every case, a protocol sheet will be placed at patient's bedside as a reference material. This is also a way to provide continuing education about the study and who should be contacted if there is a concern that escalation in narcotics use is indicated.

Blinding of the NICU staff will be maintained since in an extubated patient, there will be no way to determine allocation based on the caudal wounds. In the intubated patient it will not be clear whether the patient started out intubated or was intubated because of a caudal failure. Since the intra-operative anesthesia approach will be standardized, there will be no additional information that the NICU staff will require. The anesthesia record will be placed in a sealed envelope in the chart prior to departure from the OR. The NICU staff will be able to unseal the envelope in the event that rescue patient management is needed or if it is felt to influence management. In addition, personal contact information for the two anesthesiologists involved in the study will be provided to the staff in the event there would be an urgent question requiring clarification. The envelope label will also instruct medical records personnel to open the envelope and make contents part of the patient's medic record upon hospital discharge. A letter will be sent to parents upon discharge specifying their child's group assignment.

A research specialist and two other surgeons will have completed CITI courses and be available to give informed consent to parents for the study. Baptist IRB will be submitted for approval after acceptance by the CRRC. Cases are normally scheduled 3-7 days ahead of time so the research specialist should have sufficient time to perform the consent process. In the event that the research specialist is unavailable, another trained surgeon will be accessible. Although we will try to prevent selection bias in the NICU, there is bound to be times when parents will opt out of the randomization process and will elect to have either general anesthesia and single-shot caudal or caudal catheter infusion. Those patients will still be consented for use of their data in the study. At the time of manuscript preparation, those patients will be identified as refusing randomization.

Inguinal hernia repair will be performed by one of five pediatric surgeons employed by Nemours Children's Clinic in the same standard fashion. Key components of the operation include groin incision and a high ligation of the hernia sac, which is the standard of care in the United States. Laparoscopic inguinal hernia repair will not be performed in these patients for three reasons: Firstly, so that there is standardization among surgeons performing the operation and secondly for statistical analysis. Thirdly, there is only one surgeon that performs this operation routinely. Caudal catheter placement and infusion will be performed and monitored by [name] and [name] who are employed by Nemours Children's Clinic in the Department of Pediatric

Anesthesiology. Having a limited number of anesthesiologists performing the standardized intra-operative approach will also allow for excellent quality control of the study.

Statistical Analysis

Currently, there are no published articles in the literature to help generate a level of data which can be used to determine the power analysis. We would want a power of 80% and a significance level of 0.05 for the study and after the first 10 patients are enrolled we can calculate a reliable sample size. Based on previous studies conducted in a prospective, randomized fashion we approximate approximately 20 patients in each arm though this is only speculation until the first ten patients are enrolled (Oghazian MB, 2015) (Rakhshani A, 2015) (Mathur NB, 2015). A review from 1/1/2014 – 12/31/14 of NICU patients undergoing inguinal hernia repair at Wolfson was performed and totaled 21. We estimate approximately 80% study inclusion and 20% exclusion. [name], a Nemours statistician will perform all statistical analysis of the study and has indicated the following will be used in the analysis. Demographic and baseline data will be summarized by treatment groups, namely general anesthesia and caudal catheter groups. Quantitative variables will be summarized by mean/SE or median/interquartile range (IQ), whichever appropriate. Categorical variables will be summarized by frequencies and percentages. A chi-square or Fisher exact analysis will be used to compare the general anesthesia group and the caudal catheter infusion group in the primary outcome, which is time to return to baseline respiratory function. A Cox hazard model ratio will compare the hazard risk between the two groups and a log rank test will calculate the median time to return to baseline function. In addition, a Cox proportional hazards model will be used to compare the risk of failure between two groups. A poisson regression analysis will compare the number of bradycardic events, apneic events, catheter complications, and number of post-operative narcotic use days between the general anesthesia group and the caudal catheter infusion group. A logistic regression model will be used to compare the proportion of successful surgical completion between two groups. We estimate the study will run two years for adequate patient accrual. Data will be input by the research nurse and sent for analysis to the statistician for periodic review every three months. Primary outcomes that will be analyzed in the statistical analysis are: time to return of baseline respiratory function, successful surgical completion, catheter complications, number of apneic episodes (defined as cessation of breathing by a premature infant that lasts for more than 20 seconds and/or is accompanied by hypoxia or bradycardia), and bradycardic events (heart rate <90). Secondary outcomes are: days to hospital discharge, number of post-operative narcotic use days, operative time, mechanical ventilation days, and time to full oral feeds.

7. Possible Discomforts and Risks:

Adverse events associated with caudal catheter placement or single-shot caudal placement are very low. This procedure is routinely done in neonatal surgery. The most common complications are infection which in a large study is less than .03% and failure of adequate pain control which is less than 5%.

If, for some reason, the catheters do not work, your child will be intubated and general anesthesia will be given. The patients in the general anesthesia and single-dose caudal injection will only receive an injection after they are intubated and not placement of a catheter.

8. Possible Benefits:

We believe that this technique for pain management in preterm infants will improve post-operative complications that are common to the NICU which include decreased respiratory rate and low heart rate.

9. Conflict of Interest

No conflict of interest exists with the PI or investigators.

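### The unblinded treating anesthesiologist hand-draws from a folder stated to hold five envelopes per arm, and no concealment procedure is described, so assignments are partly predictable and a redraw could not be detected

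*Combined protocol and SAP*

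**What the plan says.** Everything on this point is in section 6 (Research Plan) of the combined protocol and SAP.

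- **The draw.** On the day of surgery, before the infant reaches the operating room, "the anesthesiologist will randomly draw an envelope from a folder that will allocate group assignment".
- **The folder.** "10 envelopes at a time will be placed in the folder, 5 will be in the awake caudal catheter group"; the remaining half of each folder is for the comparison arm. The stated purpose is to keep the arms equal; the target is about 20 infants per group. The protocol adds, in parentheses, that drawing on the day rules out bias in the talks with parents and in consent.
- **The people who draw.** Two anesthesiologists "will provide the anesthesia for both groups and will obtain anesthesia consent on the day of surgery". During the operation, "neither the anesthesiologist nor the surgeon will be blinded".
- **Research consent.** A research representative seeks it separately. Cases are normally scheduled three to seven days ahead. If the research specialist is unavailable, a trained surgeon may step in.
- **Refusal.** "there is bound to be times when parents will opt out of the randomization process". Those families choose an arm, their data are still used, and they are identified in the manuscript as having refused randomization.

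For the allocation envelopes, the plan describes no numbering, opaque or sealed form, pre-generated list, independent holder, draw log, or rule for an envelope that is opened and returned. The only sealed envelope it describes holds the anesthesia record after the operation.

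**The concern.** Concealment protects a randomized comparison only if nobody who can influence entry knows, or can work out, the next assignment. Here the composition of the folder is in the protocol, and the people who draw are also the people who see earlier results, treat the infant and speak to the parents that day. Keeping a count turns a random draw into a partly known one.

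The second problem does not depend on counting. When any envelope in a loose folder may be taken, there is no correct next envelope. An unwelcome assignment could be put back and another drawn, and nothing in the described procedure would show it.

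With about 20 infants per arm, each infant is 1/20 = 5% of an arm, and the protocol itself describes the medical conditions of these infants as multiple and varied. A few steered cases could shift the comparison, and no later analysis could reliably detect or repair that. Blinding of NICU staff protects care after surgery, not the make-up of the arms.

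**Working it through.** **The plan's own figure.** Four folders × 5 envelopes per arm = 20 per arm, or 40 infants, which agrees with the stated target. The target itself cannot be reproduced because no effect size is given; that is a separate matter.

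**Inputs.** Folder of 10 with m = 5 per arm, drawn by two anesthesiologists (section 6). Assumption: each folder is emptied before it is refilled, which the plan does not state.

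**Upper end: the person drawing knows every earlier draw in the folder.** The best strategy is to guess the arm with more envelopes left.

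- Expected correct guesses per folder = m + [2^(2m) / C(2m, m) − 1] / 2 = 5 + [1024/252 − 1]/2 = 5 + 1.53 = 6.53 of 10, or 65.3%. An exact recursion over the envelopes left gives the same value. Over four folders this is 4 × 6.53 = 26.1 of 40, against 20 by chance.
- Expected assignments already certain before the draw = 2m/(m + 1) = 10/6 = 1.67 per folder, or 4 × 1.67 = 6.7 of 40.
- Probability that the last k envelopes are all of one arm = 2 × C(10 − k, 5 − k) / C(10, 5). For k = 1 this is 1: the tenth assignment is always known. For k = 2 it is 2 × 56/252 = 44.4%. For k = 3 it is 2 × 21/252 = 16.7%.

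**Lower end: the two split cases at random and never share results.** Each guesses only from the draws made personally. Simulating 100,000 folders gives 56.7% correct guesses and about 0.05 certain assignments per folder, or about 4 × 0.05 = 0.2 of 40.

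**Benchmark.** With full concealment the guess rate is 50% (20 of 40) and no assignment is certain.

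| Knowledge of earlier draws | Correct guesses | Certain per 10 | Certain per 40 |
|---|---|---|---|
| None (concealed) | 50% | 0 | 0 |
| Own draws only | 56.7% | 0.05 | 0.2 |
| All draws | 65.3% | 1.67 | 6.7 |

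**Where foreknowledge could act.** Set side by side, the passages leave three openings:

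1. Anesthesia consent and the draw both fall on the day of surgery and involve the same people. Their order is not stated.
2. Operating surgeons see the assignments of their own cases and share in the decision that repair is warranted. Surgeons may also act as back-up consenters, and the plan does not say that these are different surgeons.
3. Families may leave randomization and choose an arm. No rule says that an opened envelope fixes the infant as randomized, so a departure after the draw could be recorded like any other refusal.

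**The case against.** The best defence is timing. A research representative normally seeks research consent days before the draw, so most families decide before anyone holds an envelope. The parenthetical remark suggests that the authors meant the draw to come after the discussions with parents. The plan discusses opting out alongside research consent, not at the anesthesia consent on the day, and infants who opt out are to be identified in the manuscript. All of this stands and lowers the risk. It does not remove it: a late draw protects only if the result cannot be anticipated, and with a known folder it partly can be.

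Three stronger readings are tempting, and the documents do not support them.

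- **That assignments are simply predictable, at 65%.** That figure needs every earlier draw to be known. Two anesthesiologists share the cases, and nothing says that they count or compare results.
- **That the envelopes are unnumbered and there is no audit trail.** The plan is silent on numbering; the accurate statement is that none is described. There is a record of the arm received: the anesthesia record enters the chart at discharge and a letter tells the parents the assignment. Neither documents the draw.
- **That selection bias does enter.** No passage shows steering, or parents leaving at the anesthesia consent. It could enter; that is all that can be said.

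**Conclusion.** The concern holds as a weakness in allocation concealment. As written, the procedure lets an unblinded treating clinician anticipate part of the sequence: about 57% to 65% correct guesses, and about 0.05 to 1.67 certain assignments in each ten. The ends of the range rest on no sharing and full sharing of earlier results, and both assume that a folder is emptied before it is refilled. Separately, a redraw or swap could not be detected from the procedure as described, whatever the guess rate. The protocol's assurance that the timing of the draw rules out bias is therefore not secured by its own steps. This should be corrected before enrolment, but it is not evidence that any case would be steered.

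**What to change.** Replace the hand draw in section 6 with the following.

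- The trial statistician prepares a computer-generated sequence, placed in sequentially numbered, opaque, sealed envelopes.
- The research specialist holds them, outside the anesthesia and surgical teams. The block structure is removed from the protocol and not disclosed to those teams.
- The next number is opened only after research and anesthesia consents covering both arms are signed, and the infant's study number and date are written on the envelope.
- A log is kept. Any infant whose envelope is opened counts as randomized and is analysed in that arm.
- The statistician chooses the blocking, and extends the sequence if the sample size changes after the first ten patients, as the Statistical Analysis subsection foresees.

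A smaller fixed block would not help if it is known: guessing rises to 68.3% for blocks of six and 70.8% for blocks of four. A single list of 40 is not required. It lowers guessing to 58.7% and certain assignments to 2 × 20/21 = 1.9 of 40, but it presumes a sample size that the plan itself calls speculative, and it gives up early balance. The SD of the difference in arm sizes after n infants is 2 × √[n × 0.25 × (40 − n)/39]: 2.77 at 10 infants (with a 27% chance of a 7/3 split or worse), 3.20 at 20 and 2.29 at 34. The protection comes mainly from the numbered, sealed envelopes and the order of steps.

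**Cost.** A little statistician and research-specialist time, including cover on operating days, and, if blocks are varied or dropped, arm sizes that are not exactly equal at each ten.

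### The post-operative blind seals only the anesthesia record; nothing keeps the arm out of the unblinded surgeon's operative report or verbal hand-off

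*Combined protocol and SAP*

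**What the plan says.** All of the blinding text is in section 6 (Research Plan) of the combined protocol and SAP.

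- **Who knows the arm.** "Intra-operatively, neither the anesthesiologist nor the surgeon will be blinded since they are present from the induction of anesthesia until the conclusion of the operation".
- **Who does not.** "The pre-operative, intra-operative, and post-operative care by the NICU will be blinded".
- **Why the blind is expected to hold.** The wounds left by the caudal are said not to reveal the arm: "Blinding of the NICU staff will be maintained since in an extubated patient, there will be no way to determine allocation based on the caudal" [...]. For an infant who arrives intubated, the plan argues that staff cannot tell a planned intubation from one that followed a failed caudal.
- **What is concealed.** "The anesthesia record will be placed in a sealed envelope in the chart prior to departure from the OR". NICU staff may open the envelope if "rescue patient management is needed or if it is felt to influence management". Medical records staff open it at discharge.
- **Other contact with unblinded staff.** "personal contact information for the two anesthesiologists involved in the study will be provided to the staff" for urgent questions.

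The Statistical Analysis part of section 6 names the time until baseline respiratory function returns as the primary outcome. It also states: "Secondary outcomes are: days to hospital discharge, number of post-operative narcotic use days, operative time, mechanical ventilation days, and time to full oral feeds".

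**The concern.** By sealing the anesthesia record, the plan accepts that a document in the chart can reveal the arm. Two clinicians leave the operating room knowing the arm, the anesthesiologist and the surgeon, and the plan conceals only the anesthesiologist's record. The reasons given for the blind (similar caudal wounds, ambiguous intubation status, a sealed record) do not bear on what the surgeon writes or says.

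Several analysed outcomes depend partly on staff decisions as well as on the infant's physiology: when respiratory support is stepped down, when feeds are advanced and when the infant goes home. The protocol states in section 5 (Specific Aims) that it expects the catheter arm to do better. Staff who know the arm could, without intending to, act sooner for infants in that arm. A difference in the primary outcome could then reflect the management of the infants as well as the anesthetic.

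**Working it through.** No arithmetic applies, because the point depends on no sample size, error rate or event count. The check sets the texts side by side.

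**Step 1: which routes from the operating room to the NICU does the plan close?**

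| Route | What section 6 says | Closed? |
|---|---|---|
| Caudal wound | Does not reveal the arm | Yes, by the plan's argument |
| Arrival intubated | Arm is ambiguous | Yes, by the plan's argument |
| Anesthesia record | Sealed until discharge, with access if needed | Yes, unless opened |
| Surgeon's operative report | Not mentioned | No |
| Verbal hand-off | Not restricted | No |

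The nearest text to a hand-off rule is the remark that, because the anesthetic approach is standardized, NICU staff will need no further information. That is a statement about need. It does not limit what is written or said.

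**Step 2: what has to be assumed for the open routes to matter?** For the report, two things that the documents do not state: that it enters the open chart before discharge, and that it names the anesthetic technique or gives detail from which the arm can be inferred. For the hand-off, that the technique is mentioned. If these hold, the report or hand-off reveals the arm for extubated infants. It also removes the ambiguity that the plan relies on for intubated ones.

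**Step 3: which outcomes are exposed?**

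| Outcome | Protection stated in the documents apart from the blind | Exposure |
|---|---|---|
| Return to baseline respiratory function (primary) | None for the decision in the NICU | Exposed |
| Mechanical ventilation days | Extubation attempted in every infant before transport, with a 30-minute limit | Exposed for decisions after transport |
| Full oral feeds | None | Exposed |
| Days to discharge | Eligibility text refers to NICU discharge criteria but does not set them out | Exposed |
| Narcotic use days | Same FLACC-based rule in both arms and a bedside protocol sheet | Partly protected; FLACC is scored by an observer |
| Apnea, bradycardia | Stated definitions: over 20 seconds and/or with hypoxia or bradycardia; heart rate below 90 | Partly protected |

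**Step 4: can the bias be sized?** No. That would need the share of infants whose arm becomes known and the shift in each outcome when it does. The documents give neither.

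**The case against.** The strongest reply is that the harm rests on silence. Section 6 assigns post-operative care to the NICU and describes no surgical role after the operation. It also does not say that an operative report is filed openly. This stands: leakage is a risk that the plan leaves open, and not a practice that it describes.

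Three stronger readings are tempting, and the documents do not support them.

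- *The surgeon shares in post-operative decisions.* A reader might infer this from the words "When the NICU staff and surgeon decide that inguinal hernia repair is warranted", or from the principal investigator's department being pediatric surgery. The quoted words concern the decision to operate, made before consent and allocation. Neither text shows a part in later decisions on feeding, analgesia, respiratory support or discharge.
- *The blind is the only protection against biased decisions.* It is not. The common pain rule, the bedside sheet, the extubation attempt in all infants and the apnea and bradycardia definitions all limit discretion.
- *The false-positive rate rises by a stated amount.* Any such figure would rest on an invented shift and an invented share of unblinded infants. A t-test illustration would also use a test that the plan does not name; it lists chi-square or Fisher, Cox, log-rank, Poisson and logistic methods.

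It may also be said that the plan itself provides other routes to the arm, through discretionary unsealing and direct contact with the unblinded anesthesiologists. That is true, and the fix below leaves both in place. They serve urgent or management needs, whereas an open operative report could reveal the arm with no such need. They are no reason to leave that gap.

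**Conclusion.** The point holds as an incomplete safeguard. The plan says that NICU blinding will be maintained, yet it conceals the record of one of the two unblinded clinicians and says nothing about the other's report or about the hand-off. The exposed outcomes include the primary one. How far the arm would become known depends on the assumptions that the report is filed openly, and that the report or hand-off discloses the technique. The size of any resulting bias cannot be estimated from the documents. Narcotic use, apnea and bradycardia are less exposed than respiratory recovery, ventilation days, feeding and discharge. The documents do not support a conclusion that NICU care would in fact be unblinded, or that surgeons would steer outcomes.

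**What to change.** In the blinding text of section 6, extend the existing concealment to the surgeon's documents:

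- The operative report and the hand-off to the NICU describe the anesthetic only as 'anesthesia per study protocol'.
- Any detail that would reveal the arm goes into the sealed envelope already used for the anesthesia record, with the same access for rescue and the same opening at discharge.

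This takes a few sentences and a standard phrase for the report. The downside is small: the anesthetic technique is absent from the open operative report until the envelope is opened. No change is needed to treatment, to who makes post-operative clinical decisions, to the sample size or to the analysis.
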